#### b. Hepatitis C Recurrence or Flare

Subjects who achieved SVR 12 and subjects with ongoing HCV infection are eligible for enrollment. In rare circumstances, HCV subjects who achieve SVR 12 may relapse at later time points. Relapse is characterized by detection of HCV RNA, often accompanied by ALT elevations to  $> 5 \times \text{ULN}$ . In the absence of hepatic decompensation, ALT/AST elevations are typically isolated (ie, limited/no elevations of bilirubin/ALP).

Among subjects with uncontrolled hepatitis C, virologic flares are possible. Hepatitis C flares are characterized by rapid elevations of ALT and AST to  $> 5 \times \text{ULN}$  and/or  $> 3 \times$  baseline along with an increase in HCV RNA. ALT elevation to  $\geq 10 \times \text{ULN}$  and a 1 log elevation in HCV RNA level are common. In the absence of hepatic decompensation, ALT/AST elevations are typically isolated (ie, limited/no elevations of bilirubin/ALP). Laboratory abnormalities secondary to flare or recurrence are typically observed for 3 to 5 weeks.

Guidelines for subjects with recurrent HCV infection or an HCV flare are described below:

##### i. Recurrent HCV infection:

If the subject entered the study with an HCV RNA test of “Target not Detected” and has confirmed detectable HCV RNA (2 specimens, 1 week apart), then the subject has experienced a late HCV relapse or a recurrent infection.

- Question the subject about use of injection or inhalation drugs.
- At the time of first detection of HCV RNA, send a specimen for HCV genotyping.
- Measure AST, ALT, ALP, Tbil, Dbil, and INR weekly.
- Measure HCV RNA levels every 2 weeks.
- Therapy with HCV antiviral treatments should be strongly considered.

ii. HCV Flare:

- At the time of first detection of HCV RNA, send a specimen for HCV genotyping.
- Measure AST, ALT, ALP, Tbil, Dbil, INR weekly.
- Measure HCV RNA levels every 2 weeks.
- Therapy with HCV anti-viral treatments should be strongly considered.

iii. For both recurrent infection and HCV flare: if ALT returns to normal or Grade 1 (if normal at baseline), or to baseline grade (if Grade 2 at baseline) within 12 weeks, and the subjects are clinically stable, subjects may restart study treatment. If these conditions are not met, then study treatment should be permanently discontinued.

c. Immune-Related Hepatitis

i. Description: Immune-related hepatitis due to study treatment should be suspected if any of the following is seen:

- AST or ALT baseline values are less than  $2 \times \text{ULN}$ , and AST or ALT laboratory values increase to  $\geq 5 \times \text{ULN}$ .
- Among subjects with baseline ALT or AST  $\geq 2 \times \text{ULN}$ , levels increase to  $> 3 \times$  the baseline level.
- AST/ALT  $> 500 \text{ U/L}$  regardless of baseline level.
- Among subjects with baseline Tbil levels  $< 1.5 \text{ mg/dL}$ : a value of  $> 2.0 \text{ mg/dL}$ .
- Among subjects with baseline Tbil levels that are  $\geq 1.5 \text{ mg/dL}$ : a value of  $\geq 2 \times$  the baseline level.
- Total bilirubin  $> 3.0 \text{ mg/dL}$  regardless of baseline level.

Immune-related hepatitis is a diagnosis made after excluding other possible etiologies for the change. Viral flare (if applicable), biliary or vascular obstruction, infection, medications, and alcohol use must be ruled out (see below).

ii. Management

- Interrupt study treatment and alert the sponsor as per ECI criteria above for ALT, AST, bilirubin, and hepatic decompensation.
- Start IV corticosteroid (methylprednisolone 125 mg or equivalent) followed by oral corticosteroid.
- Monitor with biweekly laboratory tests including AST, ALT, Tbil, Dbil, ALP, and INR.
- If symptoms and laboratory tests resolve to Grade  $\leq 1$  or baseline (if abnormal at baseline), taper steroids over 28 days. Study treatment may be restarted after steroid treatment has been tapered to prednisone  $\leq 10 \text{ mg/day}$  (or equivalent dose of another agent). Treatment and laboratory results must be reported on a case report form (CRF).

- If laboratory abnormalities do not resolve within 3 weeks, or steroids cannot be lowered to  $\leq 10$  mg/day (or prednisone equivalent) within 12 weeks, or subjects show evidence of decompensation to CP C status or have esophageal or variceal bleeding at any point, treatment must be permanently discontinued. This must be reported on a CRF.

d. Other Hepatic Adverse Events

- Infection needs to be ruled out with cultures of blood, urine, and ascites (if possible), as well as chest x-ray and abdominal imaging if relevant. If an infection is found, antibiotics should be started.
- If Tbil is elevated above baseline, magnetic resonance cholangiopan-creatography or ultrasound with Doppler should be obtained to rule out vascular compromise, biliary obstruction, and/or tumor progression. If biliary obstruction is present, consultation with a gastroenterologist and/or an interventional radiologist should be obtained to see if the obstruction may be relieved.
- A careful review of drugs, including herbal and alternative medications, should be obtained, and alcohol use should be ruled out.
- For all of these cases, subjects may resume study treatment if they are clinically stable after appropriate therapy or discontinue the causative agent, as long as laboratory values have returned to Grade 1 or baseline (if normal or Grade 1 at start) or to baseline grade within 3 weeks.
- Treatment must be permanently discontinued if the subject is off study treatment therapy for infection, obstruction, or drug/alcohol-related toxicity for more than 3 weeks, or if they have esophageal bleeding, or become CP C at any point.

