  - CP score of A within 7 days of first dose of study drug ([Appendix I](#)).
  - Subjects may have received no more than 2 lines of prior therapy for the advanced disease (If a subject progressed within 6 months of completing adjuvant therapy, this would count as a prior line of therapy).
  - Must have progressed on, refused, or were intolerant of sorafenib. If the subject received sorafenib, it must be at least 14 days since prior treatment with sorafenib before first dose of study treatment.
    - Intolerant is defined as any Grade  $\geq 2$  drug-related AE that, despite supportive therapy, recurred after sorafenib treatment interruption of at least 7 days and dose reduction resulting in the subject requesting or the physician recommending discontinuation due to toxicity.

- The following are excluded: Subjects with liver transplants, clear invasion of the bile duct or main portal branch(es), or hepatorenal syndrome, or subjects who have required esophageal variceal ablation within 28 days of starting study treatment.
  - Has been treated with anti-hepatitis B therapy. Subjects with controlled (treated) hepatitis B will be allowed if they meet the following criteria:
    - Antiviral therapy for hepatitis B virus (HBV) must be given for at least 12 weeks, and HBV viral load must be < 100 IU/mL before the first dose of study drug. Subjects on active HBV therapy with viral loads < 100 IU/mL should stay on the same therapy throughout study treatment.
    - Subjects who are anti-HBc positive, negative for HbsAg, negative for anti-HBs, and have an HBV viral load < 100 IU/mL do not require HBV antiviral prophylaxis.
  - Subjects with history of hepatitis C virus (HCV) who have had successful treatment, defined as undetectable HCV RNA more than 12 weeks after treatment (these subjects may be HCV antibody positive, but will not have detectable RNA). Also subjects with untreated HCV and those who failed treatment are permitted. However, for those with untreated HCV and those who have failed treatment, HCV viral load (HCV RNA) will be monitored every cycle.
  - Blood pressure must be adequately controlled (blood pressure medications have been stable for 1 month).
  - Albumin  $\geq$  3.0 g/dL. NOTE: No albumin supplement (or BCAA) allowed within the last 14 days.

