## APPENDIX I. CHILD-PUGH SCORE

### Child-Pugh Score

Measure	1 Point	2 Points	3 Points
Total bilirubin, $\mu\text{mol/L}$ (mg/dL)	< 34 (< 2)	34-50 (2-3)	> 50 (> 3)
Serum albumin, g/dL	> 3.5	2.8 – 3.5	< 2.8
Prothrombin time, prolongation(s)	< 4.0	4.0 – 6.0	> 6.0
Ascites	None	Mild (or suppressed with medication)	Moderate to Severe (or refractory)
Hepatic encephalopathy	None	Grade I-II	Grade III-IV

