## **APPENDIX J. GUIDANCE FOR DIAGNOSIS AND MANAGEMENT OF HEPATIC EVENTS IN SUBJECTS WITH HCC**

All of the events listed below will require holding study treatment, notification of the sponsor within 24 hours, and a hepatology consultation. All cases should be entered into EDC and recorded as events of clinical interest/immune AEs. All cases of re-treatment and permanent discontinuation must be reported to the sponsor and recorded in the database.

- a. ALT:
  - i. Among subjects with baseline ALT  $< 2 \times$  ULN: ALT  $\geq 5 \times$  ULN
  - ii. Among subjects with baseline ALT  $\geq 2 \times$  ULN: ALT  $> 3 \times$  the baseline level
  - iii. ALT  $> 500$  U/L regardless of baseline level
- b. AST:
  - i. Among subjects with baseline AST  $< 2 \times$  ULN: AST  $\geq 5 \times$  ULN
  - ii. Among subjects with baseline AST  $\geq 2 \times$  ULN: AST  $> 3 \times$  the baseline level
  - iii. AST  $> 500$  U/L regardless of baseline level
- c. Total bilirubin:
  - i. Among subjects with baseline levels  $< 1.5$  mg/dL: a value of  $> 2$  mg/dL
  - ii. Among subjects with baseline levels that are  $\geq 1.5$  mg/dL: a value  $\geq 2 \times$  the baseline level
  - iii. Total bilirubin  $> 3.0$  mg/dL regardless of baseline level
- d. Regardless of laboratory values, hepatic decompensation diagnosed clinically, including:
  - i. New onset clinically detectable ascites
  - ii. Gastrointestinal bleeding suggestive of portal hypertension (e.g., esophageal or gastric varices)
  - iii. Hepatic encephalopathy

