### **Permanent Discontinuation Criteria for Subjects with Hepatic Adverse Events**

Therapy should also be **permanently discontinued** for any of the following:

- ALT  $> 20 \times$  ULN
- CP score of  $\geq 9$  points
- Gastrointestinal bleeding suggestive of portal hypertension (eg, esophageal or gastric varices)
- New onset of clinically detectable ascites
- Hepatic encephalopathy
- Recurrence of a severe or life-threatening event, or of any of the laboratory abnormalities listed above, that are presumed to be immune-related

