#### **a. Hepatitis B Flare**

Hepatitis B flares are characterized by rapid elevations of ALT and AST to  $> 5 \times$  ULN and/or  $> 3 \times$  baseline. ALT elevation to  $\geq 10 \times$  ULN is common. In the absence of hepatic decompensation, ALT/AST elevations are typically isolated (ie, limited/no elevations of bilirubin/ALP). Subjects who are compliant with antiviral therapy should have continued suppression of HBV DNA at the time of flare; thus, detection of HBV DNA should prompt

questioning of subjects for compliance. Laboratory abnormalities secondary to flare are typically observed for 3 to 5 weeks.

Among subjects with HBV, a flare should be considered if this pattern is observed and there is no evidence of an alternative etiology. Guidelines for subjects with a diagnosis of HBV flare are as follows:

- Care should be instituted in consultation with a hepatologist.
- For subjects who have detectable HBV DNA, reinstitute antiviral therapy.
- If the subject is clinically stable, study drug administration may be interrupted for up to 12 weeks. Subjects should undergo weekly laboratory tests, including AST, ALT, ALP, Tbil, Dbil, INR, HbsAg, HBV DNA (if detected at the onset of the flare). Obtain anti-Hbe, anti-HBs, and HBV DNA levels (if not detected at the onset of the flare) every 2 to 3 weeks.
- If ALT returns to normal or Grade 1 (if normal at baseline), or to baseline grade (if Grade 2 at baseline) within 12 weeks, and subjects are clinically stable, subjects may restart study treatment. If these conditions are not met, then study treatment should be permanently discontinued.

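### Appendix J lets treatment restart after a viral hepatitis flare on ALT and clinical stability alone, without saying that the AST and total bilirubin holds must also have cleared

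*Protocol*

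**What the plan says.** **Hold.** Appendix J opens with a mandatory rule: "All of the events listed below will require holding study treatment, notification of the sponsor within 24 hours, and a hepatology consultation". Four groups of triggers follow, each sufficient alone:

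- ALT: at least 5 × ULN if baseline is below 2 × ULN; more than 3 × baseline if baseline is 2 × ULN or higher; above 500 U/L at any baseline.
- AST: the same three thresholds, in a separate list whose first entry begins "Among subjects with baseline AST".
- Total bilirubin: above 2 mg/dL if baseline is below 1.5 mg/dL; at least 2 × baseline if baseline is 1.5 mg/dL or higher; above 3.0 mg/dL at any baseline.
- Clinical decompensation: new ascites, bleeding that suggests portal hypertension, or encephalopathy.

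**Restart after a viral event.** The hepatitis B rule (item a) reads "If ALT returns to normal or Grade 1 (if normal at baseline), or to baseline grade" where baseline was Grade 2. It allows 12 weeks, adds that the subject be clinically stable, and closes with "If these conditions are not met, then study treatment should be permanently discontinued". The rule shared by hepatitis C recurrence and flare (item b, iii) opens "For both recurrent infection and HCV flare: if ALT returns to normal or Grade 1 (if normal at baseline" and has the same structure. AST and total bilirubin are measured weekly during these events, but neither rule names them.

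**Neighbouring branches.** For immune-related hepatitis (item c) and other hepatic events (item d), recovery refers to laboratory results generally, not to ALT alone.

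**Permanent discontinuation.** The list contains ALT above 20 × ULN, a Child-Pugh score of 9 or more, the three decompensation signs (for example "New onset of clinically detectable ascites"), and recurrence of a severe event or listed laboratory abnormality presumed immune-related.

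**The concern.** A hold rule and its restart rule should test the same quantities, or the text should say which one governs. Here the hold has independent AST and bilirubin triggers and the restart has neither. Items a and b describe viral flares by rises in both transaminases, yet only ALT decides recovery.

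Clinical stability does not clearly fill the gap. Appendix J leaves it undefined, and item d asks for laboratory recovery in addition to it. The definitions in Sections 5.6.4 and 7.6.3.1 concern tumour progression.

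What is at stake is re-exposure of a subject with liver cancer and viral hepatitis while a liver test is still at a level that the same appendix treats as a reason to stop. Whether that happens would rest on judgement in each case.

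**Working it through.** The plan gives no figure to reproduce. The check sets the hold triggers, restart rules and other safeguards side by side. Grades are from SAP Appendix B. For ALT and AST, Grade 1 is up to 3.0 × ULN, Grade 2 is above 3.0 to 5.0 × ULN, and Grade 3 starts above 5.0 × ULN. For bilirubin, Grade 3 starts above 3.0 × ULN.

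1. **ALT: no gap.** With normal baseline, restart needs ALT ≤ 3.0 × ULN, below the 5 × ULN hold. With Grade 2 baseline, restart needs ALT ≤ 5.0 × ULN, while the hold is above 3 × baseline, so above 3 × 3.0 = 9 × ULN. The 500 U/L trigger could still be met at 5.0 × ULN only if the ULN exceeded 500 / 5.0 = 100 U/L.
2. **Decompensation: no gap.** The three listed signs all require permanent discontinuation.
3. **AST: lowest levels at which hold and restart coexist.** 5 × ULN if baseline is below 2 × ULN; otherwise above 3 × 2 = 6 × ULN.
4. **Bilirubin: lowest levels at which they coexist.** Above 2 mg/dL if baseline is below 1.5 mg/dL; otherwise 2 × 1.5 = 3.0 mg/dL.
5. **Does the discontinuation list catch these?** It has no AST limit. Bilirubin alone cannot reach the Child-Pugh limit. Criterion 10k in Section 3.2 requires "CP score of A within 7 days of first dose of study drug", which is 5 to 6 points (Appendix I). Bilirubin scores 1 to 3 points, so it adds at most 2, and 6 + 2 = 8 < 9. The laboratory-recurrence item covers only events presumed immune-related.
6. **Does the Grade 3 withhold in Section 5.6.2 catch these?** Nearly all of the AST range in step 3 is Grade 3, so it would if that clause applies to viral events. Bilirubin differs. Let U be the laboratory ULN in mg/dL, which the documents do not give. With a low baseline, values with 2 < bilirubin ≤ 3.0 × U meet the hold without being Grade 3. That window exists whenever U > 2 / 3.0 = 0.67 mg/dL.

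**Illustration (assumed values).** Baseline ALT and AST are normal and bilirubin is 1.0 mg/dL. At week 6 of the hold, ALT is 2.5 × ULN, AST 6 × ULN and bilirubin 2.5 mg/dL, with no decompensation. ALT is Grade 1, so if the subject is judged clinically stable the restart wording is met. The AST hold (6 ≥ 5) and the bilirubin hold (2.5 > 2) are also met. Child-Pugh is 2 for bilirubin plus 1 for each of the other four items, 2 + 4 = 6, so nothing requires discontinuation. AST is Grade 3, so the laboratory recovery asked for in items c and d would not have been reached.

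**The case against.** The strongest reply is that the documents should be read as a whole. The hold is mandatory and has no exemption for flares, while the restart rules are only permissive, so a subject still at a hold level stays on hold. That reading is reasonable. But the restart rules set out their own conditions and outcomes without mentioning the hold, so the text does not say which governs.

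Other provisions also stand as mitigation:

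- Section 5.6.2 withholds both drugs for nonhematologic toxicity of Grade 3 or above, laboratory abnormalities included, and requires medical monitor discussion before resuming after an interruption for liver test abnormalities. The words drug-related appear earlier in the withhold sentence and may govern the whole of it. Table 6, which asks for recovery to Grade 1 or baseline, is titled for drug-related events and refers hepatic events in these subjects to Appendix J.
- Item d requires imaging when bilirubin is above baseline, and items a and b describe flares without decompensation as typically showing little or no bilirubin rise. Many bilirubin cases would therefore be redirected. Typical is not an exclusion, however, and hepatitis C recurrence is defined by viral RNA.
- AST at 5 × ULN or more after ALT has recovered would be an unusual course. It also matches a trigger for suspecting immune-related hepatitis, whose branch needs laboratory tests generally to resolve.
- Hepatology consultation and predose laboratory review (Section 7.5.7) precede redosing, but neither sets an AST or bilirubin limit.

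Two stronger inferences are tempting and not supported. A reader might infer that AST above 3 but below 5 × ULN at restart also conflicts with the hold. It does not: criterion 8e admits subjects with HCC at AST below 5 × ULN, and no hold trigger is met there unless the 500 U/L limit is passed. Requiring Grade 1 AST would be a preference, not a repair. A reader might also measure the gap by counting hold triggers that have no matching restart limit. The triggers for each test overlap, so a count says nothing about risk.

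**Conclusion.** The point holds as an unresolved conflict of wording. After an HBV flare, or an HCV recurrence or flare, the restart conditions can be met while AST or total bilirubin is still at a hold level, and no provision expressly says that the hold prevails when the event is judged viral. The AST part is largely covered if the Grade 3 withhold in Section 5.6.2 applies. The least protected range is bilirubin above 2 mg/dL but below Grade 3.

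A reader might infer that the plan means to allow re-exposure at these levels, or that decompensated subjects may restart. Neither follows: the hold is stated without exception, and the listed decompensation signs end treatment.

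Reach is small. It is limited to HBV- or HCV-infected subjects with HCC still on treatment, in a cohort discontinued before full enrollment (Protocol Table 3) and a study closed to enrollment (Section 4.1). The documents do not say how many such subjects there are, or whether there are any. No endpoint or analysis is affected. The conclusion assumes a literal reading of the restart rules and that clinical stability does not itself imply laboratory recovery. It is a low-cost safety clarification worth making.

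**What to change.** Add the same sentence to the restart rule in Appendix J item a and in item b, iii: *Study treatment may not restart while any hold criterion listed above (ALT, AST, total bilirubin or hepatic decompensation) is still met.*

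This resolves the conflict by itself, with no new grade threshold for AST or bilirubin. It costs one sentence in two places and no extra tests, because AST and total bilirubin are already measured weekly during these events. The downside is that some subjects will restart later, or will be discontinued because a hold level persists through the 12-week limit.

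### Appendix J sets the Child-Pugh stop at 9 points or more in its general list but at class C (10 to 15 points) in sections c and d, so a subject who reached exactly 9 and recovered could be restarted in error

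*Protocol*

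**What the plan says.** Appendix J covers hepatic events in subjects with HCC. Table 6 in Section 5.6.2 sends sites there for hepatic adverse events in these subjects, so it is operative text and not part of the amendment summary.

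- **General list** (Permanent Discontinuation Criteria for Subjects with Hepatic Adverse Events). It opens "Therapy should also be permanently discontinued for any of the following" and gives six criteria, not limited by cause: ALT above 20 times the upper limit of normal, "CP score of $\geq 9$ points", gastrointestinal bleeding suggestive of portal hypertension, new clinically detectable ascites, hepatic encephalopathy, and recurrence of certain events presumed immune-related.
- **Section c** (Immune-Related Hepatitis, Management). After laboratory recovery, "Study treatment may be restarted after steroid treatment has been tapered to prednisone" at 10 mg/day or less. The permanent stop applies if abnormalities do not resolve within 3 weeks, if steroids cannot be lowered enough within 12 weeks, or if "subjects show evidence of decompensation to CP C status or have esophageal or variceal bleeding at any point".
- **Section d** (Other Hepatic Adverse Events). Once laboratory values have recovered within 3 weeks, "subjects may resume study treatment if they are clinically stable after appropriate therapy or discontinue the causative agent". The permanent stop applies after more than 3 weeks off treatment for the listed causes, "or if they have esophageal bleeding, or become CP C at any point".
- **Appendix I** defines Child-Pugh class A as 5-6 points, class B as 7-9 and class C as 10-15.

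**The concern.** One stopping threshold appears as two numbers within the same appendix. Sections c and d each repeat two of the six general criteria, Child-Pugh and bleeding, but state the Child-Pugh one at a looser level. Each also has its own restart conditions, and neither refers to the general list. The paragraph that introduces sections a to d presents them as further guidance without saying that the list still applies.

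At stake is a subject whose liver function worsens to 9 points during a hepatic event and whose laboratory values then recover. The general list makes reaching 9 a reason to stop permanently and does not require the score to persist. Under section c or d the class C stop has not been met, and the restart conditions can be satisfied. A site working from the section that matches its diagnosis could therefore resume treatment contrary to the general list.

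**Working it through.** There is no planned figure to reproduce. The check maps both cut-offs onto one scale.

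**Inputs.** Appendix I: five items scored 1 to 3 each; classes A 5-6, B 7-9, C 10-15. Appendix J general list: stop at 9 or more. Appendix J sections c and d: stop at class C. Section 3.2, inclusion criterion 10k: class A at entry.

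**Range of the score.** Minimum 5 × 1 = 5 and maximum 5 × 3 = 15, so there are 15 − 5 + 1 = 11 possible totals.

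**Totals at which each rule stops.**

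| Rule | Totals that stop | Count |
|---|---|---|
| General list, 9 or more | 9 to 15 | 15 − 9 + 1 = 7 |
| Sections c and d, class C | 10 to 15 | 15 − 10 + 1 = 6 |

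The difference is 7 − 6 = 1 total, namely 9. At 8 or below neither rule stops on Child-Pugh grounds; at 10 or above both do.

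**Distance from entry.** Entry is 5 or 6 points, so reaching 9 is a rise of 9 − 6 = 3 to 9 − 5 = 4 points.

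**Do the other general criteria already catch a score of 9?** New ascites and encephalopathy are separate permanent stops in the list, so a 9 that includes either is caught by another criterion of that list. But 9 can also arise from laboratory items alone. With ascites and encephalopathy at 1 point each, bilirubin, albumin and prothrombin time must total 9 − 2 = 7. Scores of 3, 3 and 1 can be arranged in 3 ways and scores of 3, 2 and 2 in 3 ways, giving 3 + 3 = 6 component patterns. The gap at 9 can therefore be reached without the ascites or encephalopathy criteria.

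**Tracing one subject.** A subject with immune-related hepatitis peaks at 9 on laboratory items, recovers within 3 weeks and is tapered to 10 mg/day or less. General list: permanent stop, because 9 was reached. Section c: class C not reached, abnormalities resolved, steroids tapered, so restart is permitted. Section d gives the same contrast for another cause with recovery within 3 weeks.

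**The case against.** The strongest reply is that nothing conflicts. The general list covers all subjects with hepatic adverse events and is framed as additional; any one criterion suffices. What follows it is presented as further guidance. Neither section c nor section d says its stops are the only ones, and neither expressly permits treatment at 9 points. Sections a and b contain no Child-Pugh stop at all, which suggests that a to d were never meant as complete stopping rules. A site that ignored the list would also miss its ALT, ascites, encephalopathy and recurrence criteria. Appendix J further requires a treatment hold, sponsor notice within 24 hours, a hepatology consultation and reporting of all re-treatment.

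Most of this stands. The cumulative reading is the better one, and a reader who inferred two rules that cannot both be followed would be going too far: stopping at 9 satisfies every sentence. But the reading does not remove the defect. Sections c and d affirmatively permit restart after recovery and name a Child-Pugh level different from the list's, which invites the belief that the level was chosen for those causes. The sponsor and the hepatologist would be consulting the same two numbers.

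A reader might also infer that the list is the weaker instruction, because it uses 'should' ("Therapy should also be permanently discontinued for any of the following") while section c says "treatment must be permanently discontinued. This must be reported on a CRF" and section d says "Treatment must be permanently discontinued if the subject is off study treatment therapy". The protocol's own usage does not support that. For events unresolved within 12 weeks, the Table 8 rows for colitis, liver tests, pneumonitis and nephritis use 'must', while the general instruction under the same table uses 'should' for the same stop. The hepatitis B and C parts of Appendix J also use 'should' as their binding stop. The two words carry the same force here.

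**Conclusion.** The point holds as a minor internal inconsistency in a safety rule. The cut-offs differ at 1 of 11 possible totals, and the general list, which is the stricter, should be taken as governing. The practical risk is an erroneous restart of an HCC subject who reached exactly 9 points, mainly through laboratory items, and then recovered.

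The affected group is small. Only HCC subjects still on treatment are exposed. The cohort was planned at 32 and discontinued before full enrollment (Section 4.1.2, Table 3), and Amendment 10 closed the study to enrollment (Section 4.1). The documents do not say how many such subjects remain or how often a score of 9 occurs, so the expected number of affected subjects cannot be calculated.

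The conclusion assumes that the general list means what it says at 9 points and applies once that score is reached. It should not be read as a challenge to the trial design or its efficacy conclusions: the rule governs whether treatment resumes, and the sample size, the definition of objective response rate and the planned analyses do not depend on it.

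**What to change.** In Appendix J, section c, replace the reference to class C status with a CP score of 9 points or more. In section d, replace the reference to becoming class C with reaching a CP score of 9 points or more. In the paragraph introducing sections a to d (Diagnosis and Management of Hepatic Adverse Events), add one sentence: the permanent discontinuation criteria listed above apply throughout sections a to d and override the restart permissions in those sections.

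The cost is two phrase replacements and one added sentence. No new stopping threshold is introduced, since the general list already stops at 9, and data collection, sample size and analysis do not change. Amendment 10's stated purpose includes guidance for subjects still on study, so a single clear stop for them is within its scope.
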